### 3.2. Inclusion Criteria

No subject will be assigned to treatment until all eligibility criteria have been satisfied. To qualify for the study a subject must:

1. Be able to provide voluntary written informed consent prior to the initiation of any study specific procedures per the policy of the governing Institutional Review Board (IRB)/ Independent Ethics Committee (IEC).
2. Be female and at least 18 years of age at the time of consent.
3. Have evidence of cellulite in 2 bilateral treatment areas (defined as right and left buttocks OR right and left posterolateral thighs) as assessed by the Investigator at the Screening visit, and fulfills the following requirements:
  - a. has a score of 2 (mild), 3 (moderate) or 4 (severe) as reported by the Investigator (CR-PCSS) in 2 treatment areas (two thighs or two buttocks) at the Screening Visit.
  - b. has at least 2 dimples from each treatment area that:
    - are isolated and separated by at least 5 cm from any other dimples
    - score 2 or 3 on the Hexsel depression scale
    - have dimple width: length ratio  $\geq 0.5$
4. Be willing to apply sunscreen to the dosing areas before each exposure to the sun while participating in the study (ie, screening through end of study).
5. Be judged to be in good health, based upon the results of a medical history, physical examination, and laboratory profile at screening.
6. Have a negative serum pregnancy test at the Screening Visit and negative urine pregnancy at Day 1 (before injection of study drug), be using an effective contraception method (eg, abstinence, intrauterine device, hormonal [estrogen/progestin] contraceptives, or double barrier control) for at least 1 menstrual cycle prior to study enrollment and through Day 71; or be menopausal defined as at least 12 months of amenorrhea in the absence of other biological or physiological causes (as determined by the Investigator), or be post-menopausal for at least 1 year, or be surgically sterile (hysterectomy, bilateral oophorectomy, bilateral tubal ligation).
7. Be willing and able to comply with all protocol required study visits and assessments.

### 3.3. Exclusion Criteria

A subject will be excluded from study participation if she:

1. Is pregnant or is intending to become pregnant during the study.
2. Is presently nursing/breastfeeding or providing breast milk.
3. Has any of the following systemic conditions:
  - a. Coagulation disorder.
  - b. Evidence or history of malignancy (other than excised basal-cell carcinoma) unless there has been no recurrence in at least 5 years.

- c. History of keloidal scarring or abnormal wound healing.
  - d. Concurrent diseases or conditions that might interfere with the conduct of the study, confound the interpretation of the study results, or endanger the subject's well-being. Any questions about concurrent diseases should be discussed with the Medical Monitor.
  - e. Evidence of clinically significant abnormalities on physical examination, vital signs, electrocardiogram (ECG), or clinical laboratory values.
4. Has any of the following local conditions in the areas to be treated:
    - a. History of lower extremity thrombosis or post-thrombosis syndrome.
    - b. Vascular disorder (eg, varicose veins, telangiectasia).
    - c. Inflammation or active infection.
    - d. Severe skin laxity, flaccidity, and/or sagging.
    - e. Active cutaneous alteration including rash, eczema, psoriasis, or skin cancer.
  5. Has a tattoo located within 2 cm of the site of injection.
  6. Requires anticoagulant or antiplatelet medication during the study or has received anticoagulant or antiplatelet medication (except for  $\leq 150$  mg aspirin daily) within 7 days before injection of study drug.
  7. Has used any of the following for the treatment of EFP on the area to be treated within the timelines identified below or intends to use any of the following at any time during the course of the study:
    - a. Liposuction within the treatment areas during the 12-month period before injection of study drug.
    - b. Injections (eg, mesotherapy); radiofrequency device treatments; laser treatment; or surgery (including subcision and/or powered subcision) within the treatment areas during the 12-month period before injection of study drug.
    - c. Any investigational treatment for EFP/cellulite on treatment areas during the 12-month period before the injection of study drug.
    - d. Endermologie® or similar treatments within the treatment areas during the 6-month period before injection of study drug.
    - e. Massage therapy within the treatment areas during the 3-month period before injection of study drug.
    - f. Creams (eg, Celluvera™, TriLastin®) to prevent or mitigate EFP within the treatment areas during the 2-week period before injection of study drug.
  8. Has received an investigational drug or treatment within 30 days before injection of study drug.
  9. Has a known systemic allergy to collagenase or any other excipient of study drug.
  10. Has a history of drug or alcohol abuse.
  11. Intends to initiate an intensive sport or exercise program during the study.
  12. Intends to initiate a weight reduction program during the study.
  13. Intends to use tanning spray or tanning booths during the study.

14. Has previously received any collagenase treatments (eg, Santyl® ointment and/or XIAFLEX/XIAPEX®).
15. Was a subject in a previous cellulite clinical trial of CCH: AUX-CC-830, AUX-CC-831, EN3835-102, EN3835-104, EN3835-201, EN3835-202, EN3835-205, EN3835-302, or EN3835-303.
16. Any other condition(s) that, in the Investigator's opinion, might indicate the subject is unsuitable for the study.

### **3.4. Treatment Region and Area**

Treatment region is defined as buttocks OR posterolateral thighs. A subject will have two treatment areas defined as both buttocks (left and right buttocks) OR both thighs (left and right posterolateral thighs).

### **3.5. Selection of Dimples and Injection Sites During Treatment Visits**

#### **3.5.1. Selecting and Marking the Dimples**

The investigator will select dimples in the treatment areas (left and right buttocks OR left and right posterolateral thighs) that are well defined, evident when the subject is standing in a consistent relaxed pose (without the use of any manipulation such as skin pinching or muscle contraction), and suitable for treatment. If both buttocks and both thighs meet entry criteria for a single subject, then the thighs will be treated. No subject will be treated for EFP in both the buttocks and the thighs during this study.

The Investigator will identify at least two (2) dimples per treatment area which should be spaced out by at least 5 cm from other dimples and score 2 or 3 on the Hexsel depression scale (see [Table 6](#) for Question B on Hexsel score).

### **3.6. Study Drug Administration**

Each subject will receive 24 injections for a total of 1.68 mg (0.84 mg per treatment area) at each treatment visit. The cumulative CCH dose will be 5.04 mg for each subject who completes the 3 treatment visits.

Each subject will receive study drug on Day 1, Day 22 and Day 43 (treatment visits) unless the treatment area is dimple-free at Treatment Visit 2 (Day 22) and/or Treatment Visit 3 (Day 43). A dimple-free buttock or thigh at Treatment Visit 1 (Day 1) is precluded by the eligibility criteria. A dimple-free buttock or thigh at Treatment Visit 2 (Day 22) and/or Treatment Visit 3 (Day 43) does not preclude treatment of the contralateral buttock or thigh unless it is also dimple-free.

The study drug, CCH, will be administered using 1 of 5 injection techniques. Each of the injection techniques are referred to as a treatment arm (I - V). Subjects will be sequentially assigned to a treatment arm at Day 1. Injection techniques differ from each other in, concentration of the CCH injectate, angle of injection, depth of injection, volume of injection and study drug administration at injection site.

At every treatment visit, irrespective of the treatment arm (injection technique) assigned, all eligible subjects will receive the same amount of study drug (CCH, 0.84mg) injected in each

assigned treatment area. All eligible subjects with dimples (in each buttock or thigh) that require treatment to improve the aesthetic appearance will receive full treatment course with CCH injections. Across all treatment arms, study drug will be administered subcutaneously while subject is in a prone position.

The injection volume and concentration for each treatment arm are outlined in [Table 2](#) below.

**Table 2: Volume and Concentration of Injections**

Treatment	Number of Subjects/Area	Dose/ Injection	Volume/Injection	Drug Concentration/ Injection	Total Volume/ Treatment Visit
Treatment I: Shallow injection, 3 aliquots	6 (buttocks) 6 (thighs)	0.07 mg	0.3 mL (given as 3 - 0.1 mL aliquots)	0.23 mg/mL	7.2 mL (12 injections/ treatment area x 2 treatment areas x 0.3 mL)
Treatment II: Shallow injection, 1 aliquot	6 (buttocks) 6 (thighs)	0.07 mg	0.3 mL (given as 1 - 0.3 mL aliquot)	0.23 mg/mL	7.2 mL (12 injections/ treatment area x 2 treatment areas x 0.3 mL)
Treatment III: Deep injection, 1 aliquot	6 (buttocks) 6 (thighs)	0.07 mg	0.3 mL(given as 1 - 0.3 mL aliquot)	0.23 mg/mL	7.2 mL (12 injections/ treatment area x 2 treatment areas x 0.3 mL)
Treatment IV: Deep and shallow injections, 5 aliquots	6 (buttocks) 6 (thighs)	0.07 mg	1.5 mL (given as 5 - 0.3 aliquots)	0.047 mg/mL	36 mL (12 injections/ treatment area x 2 treatment areas x 1.5 mL)
Treatment V: Shallow injection, 4 aliquots	6 (buttocks) 6 (thighs)	0.07 mg	1.2 mL (given as 4 - 0.3 mL aliquots)	0.060 mg/mL	28.8 mL (12 injections/ treatment area x 2 treatment areas x 1.2 mL)

### 3.6.1. Determination of Sample Size

A sample size of 60 subjects (30 with two eligible buttocks and 30 with two eligible thighs) was chosen empirically based on the pragmatic criteria and published data of previous studies.

### 3.6.2. Blinding and Randomization

This is an open-label study. Subjects will be sequentially assigned to a treatment arm at Day 1.

### 3.7. Clinician Reported Photonumeric Cellulite Severity Scale (CR-PCSS)

The CR-PCSS - Buttock (Table 3) and the CR-PCSS - Thigh (Table 4) will be used to assess the severity of cellulite of both treatment areas respectively at Screening (each buttock or each thigh independently).

These ratings will be marked on the source documentation and then entered into the Electronic Data Capture (EDC) system.

The scale is a 5-level photonumeric scale developed specifically for clinicians and used by the Investigator to assess the severity of the subject’s cellulite in each buttock or thigh by live assessments.

The ratings range from 0 (None) to 4 (Severe) with labels and descriptors to aid the Investigator in the assessments. This assessment should be made while the subject is in the standing position with relaxed gluteus muscles. See chart below for details.

**Table 3: CR-PCSS Buttock Scale**

Rating	Level of Severity	Description
0	None	No dimples or evident cellulite
1	Almost None	Few dimples that are mostly superficial in depth
2	Mild	Several dimples of which most are shallow in depth
3	Moderate	Many dimples of which most are moderate in depth
4	Severe	A lot of dimples with some of more severe depth

**Table 4: CR-PCSS Thigh Scale**

Rating	Level of Severity	Description
0	None	No depressions or raised areas
1	Almost None	A few depressions or undulations that are mostly superficial in depth
2	Mild	Several undulations that are shallow in depth with areas of slight protuberances
3	Moderate	Many undulations with alternating areas of protuberances and depressions, of which most are moderate in depth
4	Severe	A lot of undulations with alternating areas of protuberances and depressions, some of more severe depth.

The investigator will go through a training process and will need to pass a qualifying exercise prior to using the CR-PCSS.

### 3.8. 3-D Photography

The 3-D photographs are not direct efficacy measurements; however, 3-D photography will be utilized in the assessment of treatment effect. The investigator or qualified designee will photograph each treatment area (both buttocks and both thighs) prior to injections using a Sponsor-supplied standardized digital camera in a standardized manner as per 3-D photography manual, at the following time points:

- Before and after marking dimples and injection sites on treatment Days 1, 22, and 43
- Single set of photographs will be taken at screening and all other visits

The 3-D photographs taken at Days 4, 8, 15, 22, 43, and 71 [End of Study (EOS)/Early termination) will be assessed by a central assessor blinded to the treatment arm and study visit day. The central assessor will complete a 5-point Likert Scale to gauge the level of aesthetic improvement achieved (from baseline) in each treatment area (ie, scoring from worse to very much improved, for aesthetic improvement).

The labels and descriptions associated with each level of aesthetic improvement achieved of Likert Scale are shown in Table 5 below:

**Table 5: Likert Scale of Level of Aesthetic Improvement**

Rating	Description
-1	Worse (The treated area appearance is worse than before treatment)
0	No change (The treated area appearance is essentially the same as before treatment)
1	Improved (Obvious improvement in the treated area appearance from before treatment, but additional treatment is indicated)
2	Much Improved (Marked improvement in the treated area appearance from before treatment, but not completely optimal)
3	Very much improved (Optimal cosmetic result from treatment of the treated dimples)

### 3.9. Dimple Analysis

The Image Analysis Technician (IAT) will use the Day 1-Post marking image as a reference to determine the location of the target dimple on the Day 1-Pre marking image.

A tracing will be made around the border of concavity of the dimple on the Day 1-Pre marking.

The dimple tracing will be transposed on to the Day 22-Pre Marking, Day 43-Pre marking, and Day 71/ET images.

This tracing will be used to measure the:

- Max length, the largest straight line distance across the dimple
- Max width, the largest straight line distance perpendicular to the max length measurement
- Surface area of the dimple
- Volume between the base of the dimple and the interpolated surface

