##### **4.5.2. Change in Dimple Analysis Parameters using 3-D Photographic Image**

Dimple analysis parameters, max length, max width, surface area and volume between the dimple base and interpolated surface, will be assessed by IAT in each treatment area at Day 1, Day 22, 43, and 71/ET. The change in these parameters from Day 1 will be evaluated at Day 22, 43, and 71/ET.

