#### **7.7.2. Change in Dimple Analysis Parameters using 3-D Photographic Image**

The observed and change from Day 1 pre-marking image in dimple analysis parameters, max length, max width, surface area, and volume between the dimple base and interpolated surface, will be summarized at Day 22, 43, and 71/ET by treatment area and treatment arm using descriptive statistics.

In addition, the volume and depth data will be analyzed using the linear mixed effect model described in Section 7.7.1.1.

A listing of dimple analysis parameters will be provided.

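### Max length and max width, measured from the carried-forward Day 1 tracing, cannot show a dimple shrinking or disappearing; surface area can show at most flattening

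*SAP*

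**What the plan says.** SAP 3.9 describes one tracing step: "A tracing will be made around the border of concavity of the dimple on the Day 1-Pre marking". The outline is then reused at each later efficacy visit: "The dimple tracing will be transposed on to the Day 22-Pre Marking, Day 43-Pre marking, and Day 71/ET images". The list of measurements opens with "This tracing will be used to measure the" and has four entries:

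- "Max length, the largest straight line distance across the dimple"
- a maximum width, taken at right angles to that line
- "Surface area of the dimple"
- the volume between the dimple base and an interpolated surface

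The section describes no second tracing, gives no value to record when a dimple has gone, and does not say whether surface area follows the skin relief or is projected onto a plane.

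SAP 4.5.2, under the efficacy parameters, names all four and adds: "The change in these parameters from Day 1 will be evaluated at Day 22, 43, and 71/ET". SAP 7.7.2 plans descriptive summaries by treatment area and arm of "The observed and change from Day 1 pre-marking image in dimple analysis parameters, max length, max width, surface area", with volume as the fourth. It then sends only volume and depth to the linear mixed model of SAP 7.7.1.1. The matching endpoint in Protocol 17.5 is change in dimple depth and volume; it does not mention length, width or surface area. SAP 3.6 foresees that a treatment area may be free of dimples by Day 22 or Day 43.

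**The concern.** Length and width describe how far a dimple extends. If the boundary is taken from Day 1 at every visit, the later image contributes nothing to the extent except alignment error. The plan would then tabulate change from Day 1 in quantities that cannot change through treatment, and present it as an efficacy result for five injection techniques.

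The primary objective is the treatment effect of those techniques, and one exploratory objective is the usefulness of 3-D photography. Rows of near-zero change in every arm could be read as absence of effect, or as poor sensitivity of the imaging, when they follow from the measurement rule.

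**Working it through.** The plan states no figure on this point, so there is none to reproduce. The check is geometric.

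**Inputs from the documents.** One outline drawn at Day 1; the same outline used at Days 22, 43 and 71/ET; the four parameter definitions (all SAP 3.9).

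**Assumption.** The documents give no dimple dimensions. I take the dimple as a spherical cap with rim radius a and depth h, and vary h/a. The percentages for area and volume are illustrative.

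**Step 1, max length and max width.** Both are straight-line distances set by the outline. With the outline unchanged, change = 0 whatever happens inside it, apart from registration, pose or skin-shape differences between images. This step does not depend on the assumed shape.

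**Step 2, surface area on complete flattening.** If projected, the area is that of the outline, so change = 0. If relief-following, area at Day 1 is π(a² + h²) and after flattening πa², so the fall is (h/a)² / (1 + (h/a)²):

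| h/a | Calculation | Fall in area |
|---|---|---|
| 0.1 | 0.01/1.01 | 1.0% |
| 0.2 | 0.04/1.04 | 3.8% |
| 0.3 | 0.09/1.09 | 8.3% |
| 0.4 | 0.16/1.16 | 13.8% |
| 1.0 | 1/2 | 50.0% |

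The floor is πa², never 0.

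**Step 3, a dimple that shrinks but remains.** Take a = 10 mm and h = 2 mm, so Day 1 area is 104π mm².

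- Radius and depth both halve (5 mm, 1 mm). Fixed outline: π(25 + 1) + π(100 − 25) = 101π, a fall of 3/104 = 2.9%; length and width fall 0%. Re-traced: 26π, a fall of 75%; length and width fall 50%.
- Radius halves, depth stays 2 mm. Fixed outline: π(25 + 4) + 75π = 104π, a fall of 0%. Re-traced: 29π, a fall of 72.1%.

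Under this geometry, relief-following area inside the fixed outline responds to depth but not to narrowing.

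**Step 4, volume.** V = πh(3a² + h²)/6. With a = 10 mm, halving h from 2 to 1 mm takes V from 101.3π to 50.2π mm³, a fall of 50.5%. Flattening gives 100%. Volume within a fixed outline therefore behaves as an efficacy measure should.

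**Step 5, where the affected parameters are used.**

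| Parameter | Protocol 17.5 endpoint | SAP 7.7.2 descriptive change | SAP 7.7.2 mixed model |
|---|---|---|---|
| Max length | No | Yes | No |
| Max width | No | Yes | No |
| Surface area | No | Yes | No |
| Volume | Yes | Yes | Yes |

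Depth is also a protocol endpoint and is named for the model, but it is not among the four measurements in SAP 3.9. That is a separate matter.

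**The case against.** The strongest reply has four parts.

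1. **The fixed outline is a deliberate standardisation.** SAP 3.10 uses the same device for bruises. This stands for bruise colour and for dimple volume, which are properties of what lies inside a patch. It does not carry over to the extent of the dimple.

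2. **The wording leaves room.** The distances are across the dimple and the area is of the dimple, so the transposed outline might serve only to locate it, with details in an imaging manual that is not among the documents. Some room exists, but the sentence introducing the list says that the tracing itself is used to measure. If fresh measurement was intended, the SAP needs to say so and to give a rule for a vanished dimple.

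3. **Surface area is not necessarily fixed.** This stands. A reader might infer that three of the four parameters are incapable of showing improvement. The documents do not support that: the images are 3-D, SAP 3.9 does not call the area planar, and a relief-following area does fall on flattening. Nor would every non-zero change in such an area be image error.

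4. **Little depends on these parameters.** This also stands. The study is exploratory, and no sample size, decision rule or modelled analysis uses them. A reader might infer that the primary objective, or the assessment of 3-D photography, is undermined. The documents do not support that either: the blinded Likert rating of the 3-D images, the volume analysis and the Hexsel score are untouched.

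**Conclusion.** The point holds in a limited form. On the natural reading of SAP 3.9, max length and max width cannot register a dimple shrinking or disappearing; this rests on the stated procedure alone. Surface area is undefined: it is either unable to change, or a compressed measure of flattening with a floor above 0. The range of about 1% to 14%, rising to 50% at depth/radius 1.0, depends on the assumed spherical cap and assumed dimensions.

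The result is two, possibly three, sets of uninformative descriptive summaries labelled as efficacy, not a failure of the protocol endpoints or of the modelled analyses. Severity is moderate. It should be corrected because, as written, the rule reports a vanished dimple at full Day 1 size, and the remedy is cheap.

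**What to change.** In SAP 3.9, keep the transposed Day 1 outline for volume. For max length, max width and surface area, choose one of:

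- **(a) Drop the change.** Delete change from Day 1 in these three from SAP 4.5.2 and 7.7.2, and report them at Day 1 only, as baseline descriptors. This is a wording change with no added work.
- **(b) Re-trace.** Have the technician draw the edge of the hollow afresh on the existing Day 22 and Day 43 pre-marking images and the Day 71/ET image, at the same location, recording 0 when no hollow remains. State that the technician is masked to arm and visit: SAP 3.8 states this only for the central Likert assessor, and deciding where a hollow ends is a judgement. The cost is up to about 60 subjects × 2 areas × 2 dimples × 3 visits = 720 further outlines, plus some tracing variability. No new images or visits are needed.

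If any surface area within the fixed outline is kept, state that it is 3-D area and label it a measure of flattening.

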### 3.10. Bruise Analysis

The IAT will trace the bruise on the Day 4 image in addition to an area of normal skin. The bruise tracing and normal tissue tracing will be transposed onto the Day 1-Pre Marking, Day 8, and Day 15 images.

A pair of numerical values of the mean lab color (number) value of bruised area and normal skin color value will be collected from the 3-D photographs at each imaging evaluation visit for bruising.

Bruise analysis will consist of two L\*A\*B\* color measurements. L\*A\*B\* color values will be measured within the bruised tissue and normal tissue area of interest (AOI).

